Fifteen patients will be selected based on their ability and engagement and invited to perform 10 additional 6MWT using the app and a trundle wheel simultaneously. An additional informed consent form will be sent to these patients. To those who accept, the research team will send a pre-packaged trundle wheel.

At the end of each of these tests, patients will need to share the raw data collected by the phone during the test through the app's "share" button. When prompted, users will choose to share the data through email and send them to a special address that will be set up for the purpose in Malmö. The app will automatically attach to these emails the data it used to compute the distance including the patient's geographical position (longitude, latitude, altitude, speed) and inertial sensors data (acceleration, inclination, detected steps). Patients will be instructed to also add the distance measured by the trundle wheel to the message for reference.

In order to study the accuracy under different conditions, patients will be instructed to perform 5 tests walking along paths the shape of which is known to obtain the best distance estimation (straight or gently curved paths). Patients will also perform 5 more tests walking over paths that may be more "challenging" for the app, for example those including narrow curves, U-turns or in confined spaces.

If less than 15 trundle wheels are purchased for the study, patients will be asked to send the meters back to the clinical centre once the 10 tests are completed. Trundle wheels will be then cleaned and disinfected and sent to another batch of patients until covering 15 subjects.

Towards the end of the study, patients of the subgroup will be sent an online questionnaire related to usability and acceptance to be filled in electronically. The questionnaire will be based on the validated and widely used uMARS questionnaire¹² and the Mobile Health Technology Acceptance Model (MoHTAM) questionnaire¹³.

Five to ten patients will be selected for an additional phone-based short interview. Notes from the interview will be taken and voice will be recorded if technically possible. The interview will aim at

¹² <https://mhealth.jmir.org/2016/2/e72/>

¹³ <https://ieeexplore.ieee.org/abstract/document/6149947>

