12. STATISTICS

12.1. Description of Statistical Methods

The analysis of the data involves reviewing the spreadsheet. The use of the labels will simplify analysis and will avoid manual coding. The R programming environment will be used to compute statistics.

To assess whether patients are able and willing to use a smartphone app for the 6MWT.

For each recruited patient, we will compute the number of app-based 6MWT results available since they confirmed that they have downloaded the app. From this number, we will compute a histogram of the number of available app-based 6MWT per patient and the percentage of participants who perform at least one app-based 6MWT prior to every consultation.

To assess the accuracy of the app-based measurement.

We will compare the walked distance measured by the app with the distance measured by the trundle wheel for those tests that provide both information. We will compute descriptive statistics (mean, standard deviation, percentiles) of the difference and BlandAltman plots.

To assess whether differences in distance walked according to the app altered management of patients.

We will use the codes related to clinical evaluations to compute descriptive statistics about the frequency of those evaluations and about how many of them were triggered by observed changes of the 6MWD.

To assess the usability and acceptance of the app.

We will compute descriptive statistics of the results of the usability and acceptance questionnaires. We will use thematic content analysis to analyse the interview transcripts.

To collect raw data from phones' sensors to allow the development of future algorithms for app-guided 6MWT.

We will also use the sensors data sent from patients involved in part 2 of the study to identify strategies to improve the algorithm that computes the distance. The availability of this type of data would be unique and would open interesting research in computer science and biomedical engineering. The University of Malmo is planning to experiment signal processing (Kalman filters, FIR filters) and machine learning (LSTM RNN) techniques to improve the accuracy of the current GPS-based algorithm and to explore the possibility to develop an indoor version of the algorithm based purely on the inertial sensors (acceleration).

To determine whether the use of the 6MWT reduces time spent and number in hospital visits.

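### Part 2 tests the app on favourable and challenging paths, but the accuracy analysis specifies no summary by path type and no path-type label is stated as recorded

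*Combined protocol and SAP*

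**What the plan says.** Section 9.3 (Subsequent Visits, Part 2) gives the purpose of the two path types: "In order to study the accuracy under different conditions, patients will be instructed to perform 5 tests" on straight or gently curved paths, which the protocol regards as the shapes the app measures best. Each patient then does 5 further tests on paths that may be harder for the app, "for example those including narrow curves, U-turns or in confined spaces".

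On what is sent after each test, the same section says: "The app will automatically attach to these emails the data it used to compute the distance", which covers position and inertial data. It then adds: "Patients will be instructed to also add the distance measured by the trundle wheel to the message for reference". Neither sentence mentions path type.

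Section 12.1 compares app and wheel distance "for those tests that provide both information" and continues: "We will compute descriptive statistics (mean, standard deviation, percentiles) of the difference and BlandAltman plots". It mentions no path type. The outcome tables in Sections 3 and 6, the sample size and population text (Sections 12.2 and 12.3), the data-handling text (Section 13) and the schedule of procedures add none.

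**The concern.** The design builds in a contrast that the analysis does not report. The protocol itself regards one set of paths as best for the app and the other as possibly harder, so bias or spread may well differ between them. If so, a pooled mean and pooled limits of agreement describe neither condition. They also depend on the mix of tests returned: the 5 + 5 split is fixed by design, and it shifts if fewer challenging tests come back with both readings.

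The split could be added later. However, the intended type of each test would then have to be judged from its GPS trace, without a stated rule and possibly after the differences are known. The trace also comes from the position data behind the app distance, so one position error could affect both the difference and the classification.

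This matters in practice because Section 5.4 has the clinic use app distances to detect deterioration. A reader needs to know how far the app can be off on each kind of path.

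**Working it through.** **Design count** (Sections 7 and 9.3). 5 + 5 = 10 tests per patient, which matches the stated 10. 15 × 10 = 150 paired tests at most, and 15 × 5 = 75 per path type. The plan gives no SD, bias, margin or precision target for accuracy, so it has no figure to reproduce.

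**Effect of pooling.** All biases and SDs below are assumptions. Let favourable tests have bias b1 and SD s1, challenging tests b2 and s2, and let p be the favourable share.

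- Pooled mean m = p·b1 + (1 − p)·b2
- Pooled variance = p·(s1² + b1²) + (1 − p)·(s2² + b2²) − m²
- Limits of agreement = m ± 1.96 × pooled SD
- Coverage = share of each type's normal distribution that lies inside the pooled limits

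Worked case: favourable (0 m, SD 10 m), challenging (10 m, SD 20 m), p = 0.5.

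- m = 0.5 × 0 + 0.5 × 10 = 5 m
- Variance = 0.5 × (100 + 0) + 0.5 × (400 + 100) − 25 = 275, so SD = 16.58 m
- Pooled limits = 5 ± 1.96 × 16.58 = -27.5 to 37.5 m
- Favourable alone: 0 ± 19.6 = -19.6 to 19.6 m
- Challenging alone: 10 ± 39.2 = -29.2 to 49.2 m
- Pooled minus favourable limits: lower -7.9 m, upper +17.9 m
- Pooled minus challenging limits: lower +1.7 m, upper -11.7 m
- Coverage: 99.7% favourable, 88.5% challenging

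Range at p = 0.5. Errors are the pooled limit minus the type's own limit, lower then upper, in metres.

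| Favourable / challenging (bias, SD) | Pooled limits | Error, favourable | Error, challenging | Coverage |
|---|---|---|---|---|
| (0, 10) / (10, 15) | -21.8 to 31.8 | -2.2, +12.2 | -2.4, -7.6 | 98.5% / 91.0% |
| (0, 10) / (10, 20) | -27.5 to 37.5 | -7.9, +17.9 | +1.7, -11.7 | 99.7% / 88.5% |
| (0, 10) / (0, 20) | -31.0 to 31.0 | -11.4, +11.4 | +8.2, -8.2 | 99.8% / 87.9% |
| (0, 10) / (20, 30) | -38.0 to 58.0 | -18.4, +38.4 | +0.8, -20.8 | 99.99% / 87.1% |
| (0, 15) / (20, 15) | -25.3 to 45.3 | +4.1, +15.9 | -15.9, -4.1 | 95.3% / 95.3% |
| (0, 15) / (0, 15) | -29.4 to 29.4 | 0, 0 | 0, 0 | 95% / 95% |

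In the fifth row coverage stays near 95%, but the pooled mean of 10 m is 10 m off for each type. In the last row pooling does no harm. Reversing the sign of the bias mirrors the limits and leaves coverage unchanged.

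**Unequal return.** Take the worked case with all 75 favourable but only 45 challenging pairs, so p = 75/120 = 0.625.

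- m = 0.375 × 10 = 3.75 m
- Variance = 0.625 × 100 + 0.375 × 500 − 3.75² = 235.94, so SD = 15.36 m
- Pooled limits = -26.4 to 33.9 m, with coverage 99.5% and 84.9%

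The app's behaviour is the same as in the worked case, yet the reported limits move because the mix has changed.

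**The case against.** The strongest reply is that the contrast is already declared. Section 9.3 fixes the two conditions and their purpose before any data, so a summary by condition would carry out the plan and would not be a data-driven choice. Section 12.1 is a short outline, does not say that tests are pooled, and refers to plots in the plural. This stands in part: a split is not ruled out. But none is specified, and which tests belong to which condition is left open.

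Second, the GPS trace shows the path walked and keeps its shape after anonymisation (Section 13.1), and Section 14 describes a web tool that displays paths. The path walked may even be more relevant than the one intended. Path type is therefore partly recoverable. However, no classification rule is given, a confined space may not show in a trace, and the web tool is described for suspected faulty data or misuse.

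Third, Section 9.3 (Informed Consent) mentions an extra instruction leaflet for the 15 patients. It is not among the documents and might ask for the path type. The finding is therefore that the protocol does not state it as recorded, not that it will go unrecorded.

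Fourth, accuracy is a secondary, descriptive objective with no margin or decision rule, and every magnitude above is assumed. For challenging paths the lower limit is nearly right in two of the cases (1.7 m and 0.8 m off). This limits the weight of the point, but the remedy is descriptive too.

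**Conclusion.** The concern holds. The stated purpose of the 5 + 5 design is not carried into the stated analysis, and the item needed to carry it out is not stated as recorded. It should be fixed, but it is not critical: the objective is secondary and the gap is partly recoverable from the traces.

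The size depends on values that the documents do not give. In the assumed cases with unequal SDs and an equal mix, the pooled limits cover 87.1% to 91.0% of challenging-path differences and 98.5% to 99.99% of favourable-path ones. With equal SDs and a 20 m difference in bias, coverage holds but the mean and limits are displaced for each type. With equal bias and SD there is no harm. The calculations assume normal differences within each type and do not model repeated tests within a patient.

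**What to change.** 1. In the Part 2 instructions, ask patients to state the intended path type (favourable or challenging) in the email that carries the wheel distance.
2. In Section 12.1, report the mean, SD, percentiles and Bland-Altman plot already planned, with limits of agreement, separately for favourable and challenging paths. Give the number of paired tests and of patients in each.
3. If the email request comes too late for some tests, classify them from the GPS traces by a rule fixed before the differences are examined.
4. If a confidence interval is added, base it on patients rather than on tests, because each patient contributes several tests.

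The cost is one line of instructions and one sentence in Section 12.1, with no extra tests, patients or models. The small downside is that each summary rests on up to 75 paired tests rather than 150.

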5.2. The 6MWT

To assess patient's exercise capacity, the six-minute walk test (6MWT) is a standard method used in patients with cardiopulmonary disease such as Heart Failure (HF) or Pulmonary arterial Hypertension⁸ (PAH). The 6MWT measures how far a patient can walk in 6 minutes. Walking is an activity performed every day, by most patients except for those most severely limited. By assessing patients' ability to exercise, the 6MWT provides a global assessment of respiratory, cardiovascular, neuromuscular and cognitive function. The 6MWT does not differentiate what limits the patient, nor does it assess maximal exercise capacity. Instead, the 6MWT allows the patient to exercise at a daily functional level, and is a useful tool for assessing changes after a therapeutic intervention, and correlates with a subjective improvement in dyspnoea⁹.

In PAH the 6MWT is used to evaluate patients' response to treatment, with an increase in 6MWT distance of greater than 42 m being considered a clinically significant improvement¹⁰. Furthermore, change in 6MWT distance correlates with VO2 max, NYHA class and mortality in those patients, providing an objective assessment of disease progression, prognosis and response to treatment. It is a universally accepted test as it is safe and easily performed by the patient.

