5.4. Telemedicine services for pulmonary hypertension

In a previous research project called 6APP, we designed, developed and evaluated a mobile-health “app” (a type of telemedicine where patients use their mobile phones), to allow them to perform the 6MWT in the community. We hypothesized that a test conducted by patients, in their environment, would reflect more the patient’s functional status, would free up healthcare resources and would be less stressful and costly for the patients themselves.

The app allowed patients to perform the test both indoors, by walking back and forth along a corridor of fixed length, and outdoors, using the localization system (like the GPS). In our study with 30 PAH patients, we proved that the app is accurate when used outdoors, the measurements are reliable and repeatable and the method is well-accepted by patients¹¹.

After these encouraging results, the app has been simplified and made available for free for both Android and iPhones under the name of “Timed Walk”. The original app was developed by [name] at the Institute of Biomedical Engineering of the Oxford University. The current app, which uses the same validated outdoors test approach, is instead maintained by the University of Malmo, Sweden, where [name] is currently employed.

Given the current circumstances, the PH clinic in Oxford and other cardiovascular outpatient clinics are recommending patients to use the Timed Walk app, the results of which are being used by the clinical team to assess patients in addition to their symptoms and general well-being. This is felt to be more appealing to the patients, and would reduce the time spent in hospital on the day of their outpatient appointment. The app only allows outdoor tests (as these proved to be more reliable and practical) and to share 6MWT data via email if patients want to.

¹¹ <https://mhealth.jmir.org/2020/1/e13756/> and <https://preprints.jmir.org/preprint/22748>

It has to be noted that the app is only used to identify trends and, when deterioration is detected, for example reduction in 6MWT distance walked or change in Borg score, patients are invited to the clinic for further assessment.

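### The app is meant for following change, but the planned accuracy analysis describes single tests only and does not give the measurement error of a change

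*Combined protocol and SAP*

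**What the plan says.** Section 5.4 states the intended use: "It has to be noted that the app is only used to identify trends". A detected deterioration, such as a shorter distance, leads to an invitation to clinic. Section 12.1 (management objective) counts how many evaluations were prompted by changes in distance, and one example entry in section 9.3 (Subsequent Visits) records a treatment change after a shorter distance over the preceding four weeks.

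On accuracy, section 12.1 says: "We will compare the walked distance measured by the app with the distance measured by the trundle wheel for those tests that provide both information". The output is then fixed as: "We will compute descriptive statistics (mean, standard deviation, percentiles) of the difference and BlandAltman plots". No within-patient SD, repeatability coefficient or error of a change is planned. There is no acceptance limit, and no split by path type is stated.

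The data for more will exist. In part 2, fifteen patients are "invited to perform 10 additional 6MWT using the app and a trundle wheel simultaneously". By design the ten tests are of two kinds: "patients will be instructed to perform 5 tests walking along paths the shape of which is known to obtain the best distance estimation", followed by five on paths expected to be harder for the app.

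The only change benchmark is in section 5.2, as background on pulmonary arterial hypertension (PAH): "with an increase in 6MWT distance of greater than 42 m being considered a clinically significant improvement".

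**The concern.** A trend is a comparison of tests within one patient. Its measurement error differs from the error of a single test in two ways that pull in opposite directions. An offset that stays with the patient or phone is part of the single-test spread but drops out of a within-patient comparison. Error that varies from test to test enters a two-test comparison twice. A pooled SD of app-minus-wheel differences cannot separate the two.

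At stake is what the accuracy objective can conclude. As planned, it can say how far one app reading may lie from the wheel. It cannot say whether a change shown by the app exceeds the app's own error, although the management objective counts decisions prompted by such changes. A reader who takes the Bland-Altman limits as a guide to change could be misled either way.

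**Working it through.** The documents state no accuracy SD, limit or precision target, so there is no figure to reproduce. The check shows how the planned summary relates to the error of a change.

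**Inputs from the documents.** 15 patients with 10 paired tests each, 5 per path type (section 9.3, Subsequent Visits); 42 m (section 5.2), used only as a yardstick.

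**Assumptions.** Single-test error = overall mean + patient/phone offset + test-to-test error, with independent normal terms. Total SD is s, and ρ is the share of s² due to the stable offset. Neither s nor ρ is in the documents, so both are varied.

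**Formulas.**
- Single test, 95% half-width about the mean: 1.96 × s.
- Change between two tests (mean and offset cancel): 1.96 × √(2(1−ρ)) × s = 1.96 × √2 × SDw, where SDw is the within-patient SD.
- The ratio of the two is √(2(1−ρ)): 1.41 at ρ = 0, 1 at ρ = 0.5, 0.71 at ρ = 0.75.

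**Results (95% half-widths, m).**

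| s | Single test | Change, ρ=0 | ρ=0.25 | ρ=0.5 | ρ=0.75 |
|---|---|---|---|---|---|
| 18 | 35.3 | 49.9 | 43.2 | 35.3 | 24.9 |
| 20 | 39.2 | 55.4 | 48.0 | 39.2 | 27.7 |
| 21.43 (= 42/1.96) | 42.0 | 59.4 | 51.4 | 42.0 | 29.7 |

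A simulation at s = 18 m gave change half-widths of 50.0 m at ρ = 0 and 35.2 m at ρ = 0.5, in agreement.

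With s = 21.43 m and ρ = 0, the chance that app error alone shows a change above 42 m in either direction is P(|Z| > 42/(√2 × 21.43)) = P(|Z| > 1.386) = 16.6%, or 8.3% for an apparent fall. At ρ = 0.5 the two-sided figure is 5%. For the two-test error to stay within 42 m, SDw must be at most 42/(1.96 × √2) = 15.2 m.

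**Why path type must be in the model.** Assume SDw = 10 m within path type and a mean gap of 20 m between types.
- Change on the same path type: 1.96 × √2 × 10 = 27.7 m.
- Change across path types: the 95% range reaches 20 + 27.7 = 47.7 m in the direction of the gap.
- SDw computed over all ten tests without a path term: each test lies 10 m from the patient's mean because of path, so the variance is (9 × 100 + 10 × 100)/9 = 211 and the SD is 14.5 m. The change figure becomes 1.96 × √2 × 14.5 = about 40 m, which matches neither case.

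**Precision with complete data.**
- SDw within patient and path type: 15 × 2 × (5−1) = 120 degrees of freedom. The 95% interval is about 0.89 to 1.15 times the estimate.
- One path type alone: 60 degrees of freedom, about 0.85 to 1.22 times.
- The SD of patient means: 14 degrees of freedom, √(14/26.12) = 0.73 to √(14/5.63) = 1.58 times. The between-patient component is the imprecise one.

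**The case against.** The planned method fits the objective as written. Section 6 defines accuracy as app distance against wheel distance, and a mean, SD, percentiles and Bland-Altman plots answer that. Absolute level also matters in places: one example comment in section 9.3 (Subsequent Visits) cites a distance under 300 m. This stands, and is why the single-test analysis should be kept. It does not supply the error of a change, which the use stated in section 5.4 requires.

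A reader might infer that the app will be passed as accurate against 42 m when it is not. The documents do not support that. They set no acceptance limit and compare nothing with 42 m, which is a background figure for improvement in PAH; the clinics are cardiovascular in general and the app is used to detect deterioration. Nor is the direction known: with a large stable offset the pooled SD makes the app look worse for change than it is.

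A trend may also span several tests. Comparing averages of m tests at each end divides the independent error by √m, so the two-test figures are an upper case.

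The consequences are limited. Accuracy is a secondary, descriptive outcome, an apparent deterioration leads to further assessment, and suspect tests can be inspected (section 14). These safeguards do not address a real deterioration hidden by app error. The repeatability claimed in section 5.4 for the earlier 30-patient study carries no figure, so it does not fill the gap.

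**Conclusion.** The point holds as a gap in the analysis, not in the data. The planned accuracy output cannot give the measurement error of a change, while the app is described as a tool for following change.

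The size in this study is unknown. The pooled SD understates the error of a two-test change by a factor of up to 1.41 when there is no stable offset, equals it when the offset is half the variance, and overstates it beyond that. The ±59 m and 16.6% are illustrations: they assume a two-test comparison, purely random error and an SD chosen so that the single-test limits equal 42 m. They should not be read as an expected false-alarm rate.

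All figures assume independent normal errors with common variance. They concern app-minus-wheel error only; real day-to-day variation in walking would add to the noise of an observed trend. The change is worth making because it is cheap and widens what the accuracy objective can conclude.

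**What to change.** In section 12.1, keep the Bland-Altman analysis for absolute accuracy and add a variance-components model of the app-minus-wheel difference, with patient as a random effect and path type (favourable or challenging) as a factor. Report:

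- SDw within patient and path type, overall and by path type;
- 1.96 × √2 × SDw with a 95% interval, as the error of a change between two tests on the same path type;
- the mean gap between path types;
- the between-patient (patient or phone) component, with an interval.

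State that the difference includes wheel error, and cite the 42 m of section 5.2 only as an interpretive reference for PAH, not as an acceptance limit. The model needs the path type of each test. Section 9.3 (Subsequent Visits) asks patients to add the wheel distance to their message but does not mention path type, so it should be requested or read from the position trace.

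The cost is a short calculation in R and a few sentences, with no extra patients, tests or visits. The downside is an imprecise between-patient component with 15 patients; SDw itself is reasonably precise if data are complete.

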7. TRIAL DESIGN

The study consists of 2 parts. The first consists of collecting data about the use of an app for phone-based 6MWT, the “Timed Walk” app, during the outpatient consultations (via phone or in clinic). These data will be used to understand if patients are using the app and if the measurements produced by the app are being used for clinical decisions. The data will be collected on an electronic spreadsheet, using a coding schema, which will be analysed every 3 months for quality assurance and at the end of the study for the final statistics.

The second part of the study will involve a sample of 15 patients who will be sent a trundle wheel and will be invited to perform 10 6MWT using the app and the trundle wheel simultaneously. The data collected in this way will be used to A) assess the accuracy of the app measurement and B) create a public anonymised dataset for the development of future algorithms for the 6MWT. The same group of patients will also be invited to answer a questionnaire about the usability and acceptance of the app and will be interviewed about the same topics.

This study is a collaboration between the Oxford University Hospital (OUH) Trust and Malmo University, Sweden. Malmo University is the main developer and maintainer of the Timed Walk app, and their interest focuses on the accuracy and usability of the app. The OUH Trust is, on the other hand, interested in using the app to remotely monitor their cardiac patients and assessing its impact on the management of those patients. Malmo University will therefore offer engineering work both in terms of the app and data analysis and OUH will recruit patients and collect data.

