12.2. Sample Size Estimation

For part 1, we will not use sampling as we aim to involve all patients in the cardiovascular clinics who require a 6MWT and are able to use the app.

With regards to part 2, our 15 patients cohort is in agreement with typical usability studies.

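### The accuracy analysis works test by test with no term for patient or path type and no intervals, and 12.2 gives no precision basis for using 15 patients

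*Combined protocol and SAP*

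**What the plan says.** Accuracy of the app distance against a trundle wheel is a secondary objective (section 6), and Part 2 is its only source of data. Section 7 sets the size: "The second part of the study will involve a sample of 15 patients who will be sent a trundle wheel". Under 9.3 Subsequent Visits, Part 2, these patients are "invited to perform 10 additional 6MWT using the app and a trundle wheel simultaneously". The walks are split by design. Patients are to "perform 5 tests walking along paths the shape of which is known to obtain the best distance estimation", and then: "Patients will also perform 5 more tests walking over paths that may be more" difficult for the app, such as tight curves or U-turns. That section gives the purpose of the split as studying accuracy under different conditions.

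Section 12.1 compares the two distances "for those tests that provide both information" and continues: "We will compute descriptive statistics (mean, standard deviation, percentiles) of the difference and BlandAltman plots". It does not mention repeated walks by one patient, the two path types, or any confidence interval or standard error.

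The only statement on cohort size is in 12.2: "With regards to part 2, our 15 patients cohort is in agreement with typical usability studies".

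**The concern.** The unit in 12.1 is the walk, but walks are nested in patients. All walks by one patient normally share a phone and a way of carrying it and pushing the wheel, so their differences are likely to be correlated. The plan itself allows for differences between phones: section 13.1 (Data Recording and Record Keeping, Part 2) may keep make and model so that phones can be compared.

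Four things follow if the analysis is run as worded:

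- **Weighting.** Only walks with both readings count, so a patient with 10 complete pairs weighs twice as much as one with 5.
- **Mixed error.** One SD combines between-patient error with within-patient error. Section 5.4 says the app serves only to identify trends. For a change between two walks by one patient, a constant patient or phone bias cancels, so the within-patient part is what matters.
- **Mixed conditions.** One set of limits averages favourable and challenging paths and describes neither.
- **Precision.** The reader gets no interval. If the ordinary one is added at reporting, it will be too narrow.

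Section 12.2 does not help, because a usability convention does not say how well 15 patients fix a bias or a limit of agreement.

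**Working it through.** **Inputs.** Patients n = 15 (section 7) and paired walks per patient m = 10 (9.3 Subsequent Visits, Part 2), so at most N = 15 × 10 = 150 pairs. The documents give no SD of the differences, no within-patient correlation ρ, no agreement margin and no target interval width, so there is no planned figure to reproduce. I assume ρ from 0.05 to 0.8 and complete data, and take the SD of a single difference as the unit.

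**Formulas.**

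- Design effect for the bias: DE = 1 + 9ρ. Effective number of differences = 150/DE.
- Expected pooled variance as a share of the true total: 1 − 9ρ/149.
- 95% half-width for the bias: ordinary, 1.976/√150 = 0.161 SD; patient-level, 2.145 × √(DE/150).
- 95% half-width for a limit of agreement: ordinary, 1.96 × √(1/150 + 1.96²/298) = 0.274 SD; patient-level, 1.96 × √(DE/150 + 1.96² × V/4), where V = 2(DE/10)²/14 + 2(0.9(1−ρ))²/135.
- Coverage of the ordinary 95% intervals: simulation of the 15 × 10 layout, at least 20,000 runs per value.

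| ρ (assumed) | DE | Effective n of 150 | Pooled variance too low by | Ordinary CI covers: bias | Ordinary CI covers: upper limit | Patient-level half-width: bias (SD) | Patient-level half-width: limit (SD) |
|---|---|---|---|---|---|---|---|
| 0.05 | 1.45 | 103 | 0.3% | 90% | 93% | 0.21 | 0.30 |
| 0.1 | 1.9 | 79 | 0.6% | 85% | 91% | 0.24 | 0.32 |
| 0.2 | 2.8 | 54 | 1.2% | 76% | 85% | 0.29 | 0.38 |
| 0.5 | 5.5 | 27 | 3.0% | 59% | 66% | 0.41 | 0.56 |
| 0.8 | 8.2 | 18 | 4.8% | 49% | 52% | 0.50 | 0.75 |

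In simulation, a t interval on the 15 patient means kept 95% coverage for the bias at each ρ tried from 0 to 0.7.

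**In metres, at an assumed SD of 20 m and ρ = 0.5.** V = 2 × 0.55²/14 + 2 × 0.45²/135 = 0.0462. The limit is known to 1.96 × √(0.0367 + 0.0444) × 20 = ±11 m; the ordinary formula gives 0.274 × 20 = about ±5.5 m. For the bias the half-widths are 0.411 × 20 = 8.2 m and 0.161 × 20 = 3.2 m.

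**Why the variance split matters.** With the same assumed 20 m, the 95% error in a change between two walks is 1.96 × √2 × 20 = ±55 m from the pooled SD. From the within-patient SD, 20 × √(1−ρ), it is ±50, ±39 and ±25 m at ρ = 0.2, 0.5 and 0.8. The only benchmark in metres in the documents is a gain above 42 m in PAH (section 5.2). It is not an accuracy margin, but the answer can fall on either side of it.

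**Path types.** Suppose, for illustration, equal bias on both path types and an SD twice as large on challenging paths. The pooled SD is √((1² + 2²)/2) = 1.58. The pooled limits are then 58% too wide for favourable paths and 21% too narrow for challenging ones (1.58/2 = 0.79).

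**The case against.** The strongest reply is that the plan makes no false claim of precision. A reader might infer that 12.1 treats 150 differences as independent. The text does not support that: it states no independence assumption, the figure 150 appears nowhere, and a repeated-measures form of Bland-Altman is neither named nor excluded. Nor is any interval, standard error or test planned, so the coverage losses apply only if ordinary intervals are added later. With balanced data the planned mean and SD are close to right. All of this stands.

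The size of the loss is also uncertain. At correlations of 0.05 to 0.1, a proper interval for a limit of agreement is only 1.1 to 1.2 times as wide as the ordinary one.

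Two further inferences should be avoided. One is that each patient's walks share a route: 9.3 Subsequent Visits deliberately varies the path type within patient. The other is that there are 15 independent wheels: the same section lets wheels be returned and passed on if fewer than 15 are bought.

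Finally, accuracy is secondary, and section 5.4 has patients called in for assessment when a trend worsens. That lowers the stakes. It does not supply the missing method, the separation by path type that the design was built for, or a precision basis for the 15.

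**Conclusion.** The point holds as a gap in specification, not as a demonstrated error in a planned result. Section 12.1 does not say how up to 10 walks per patient or the two path types enter the analysis, it plans no intervals, and 12.2 gives no accuracy rationale for 15 patients.

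A claim that agreement will look far more precise than it is would go too far, because it needs both an interval that is not planned and a correlation that the documents do not give. If ordinary intervals were added, the understatement would run from modest at a correlation of 0.05 to about twofold for a limit of agreement, and 2.6-fold for the bias (0.411/0.161), at 0.5. These figures assume complete data, a single exchangeable correlation and normal differences. The metre figures also assume an SD of 20 m. The gaps in weighting, error components and path type do not depend on whether intervals are reported. This is a cheap improvement worth making before analysis.

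**What to change.** **Section 12.1.** Specify Bland-Altman limits for repeated measures from the model: difference = bias + path type (favourable or challenging) + random patient effect + residual. Report bias and limits separately by path type, and let the residual variance differ between the two. Give the between- and within-patient variance components. Give 95% confidence intervals for bias and limits by resampling whole patients or by an equivalent variance-component method. State how many complete pairs each patient contributed.

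**Section 12.2.** State the precision that 15 patients give for the bias and the limits over a range of within-patient correlations, as in the table above. Keep usability practice as the rationale for the usability objective only.

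**Cost.** A few lines of R, which the plan already names, and a short addition to the text. Section 13.1 already describes an internal patient ID that groups a user's tests. Path type must be recorded for each walk if it is not already. The stated precision will be less favourable. No extra patients or walks are needed.
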